3. STUDY POPULATION

The study population is all patients aged 18 years or over attending Bristol Heart Institute for cardiac surgery between 30 March 2010 and 31 August 2012. All patients, with the exception of prisoners and those unable to give consent through mental capacity were eligible for the study.

3.1 Sample size

The study sample size detailed in the protocol (version 6, 21 March 2012) is 2400 which corresponds to the entire predicted patient throughput at Bristol Heart Institute for the 2 year study period, allowing for up to 10% of patients to opt-out.

Details regarding the sample size calculation and review are given in the SAP covering analyses of pre-operative test results.

3.2 Flow of participants

There is no study-specific follow-up for participants in the study, although clinical data extracted from the PATS database, which covers the period from admission for surgery until their date of discharge, will be used. Information collected prospectively on study subjects specifically for the study and recorded on case report forms (CRFs) relate to the period up until 12 hours after transfer to CICU.

The participant flow will be described via the flowchart (reference [Figure F1](#)).

3.3 Characteristics of non-study patients

In order to evaluate the representativeness of the study participants, demographic and clinical data recorded in PATS will be reviewed between the following groups:

1. Ineligible patients
2. Eligible patients who were not approached
3. Eligible patients who were approached but did not consent
4. Consented patients who did not provide a post-operative blood sample
5. Consented patients who did provide a post-operative blood sample where at least one laboratory test result was available

Classifications of reasons why eligible patients were not approached, and why eligible patients refused consent, or why samples were not taken from consenting patients will be documented.

STATISTICAL ANALYSIS PLAN

COPTIC: Coagulation and platelet laboratory testing in cardiac surgery
A prognostic study of associations between post-operative test results and subsequent bleeding

Formal statistical comparisons of the final analysis group compared to those eligible and not included in the analyses will be undertaken using t-tests, Mann-Whitney tests and chi-squared tests as appropriate. Comparisons between all other groups will be descriptive.

3.4 Withdrawals

Patients (or clinicians on their behalf) can withdraw from the study at any time post-consent (including prior to their surgery). The data available for analysis will depend on the timing of the withdrawal (see [section 3.6](#)). Data collected up to the point of withdrawal will be retained for the analysis.

Data on all withdrawals is captured on the patient log CRF and will be tabulated (reference [Table T1](#)) with full details given in separate listings (reference [Table T2](#)).

3.5 Protocol deviations

The protocol states that all post-operative samples should be collected after the return of cell saver and/or pump blood, and after all "routine" protamine doses have been administered. All samples that are recorded as not being collected at this specific time will be reviewed and excluded if necessary. The overlap with the return of pump blood is of particular concern.

3.6 Analysis populations

The analysis population will be defined as all eligible, consenting patients who provided a post-operative blood sample. The final datasets will be restricted to those with laboratory assay results from the post-operative sample, and CRF data and clinical data extracted from PATS and INNOVIAN in order to define the primary outcome. Any consenting patients who had a post-operative sample collected but did not undergo surgery for medical or other reasons will be excluded from the analysis population. Comparisons between those in the final analysis population and those with CRF data and clinical data extracted from PATS and INNOVIAN in order to define the primary outcome, a pre-operative sample taken but incomplete laboratory assay results will be compared using standardised mean differences.

Involvement in any other UHBristol Clinical Trials and Evaluation Unit (CTEU) studies will be reviewed and any interventions deemed to have an impact will be reported. Details on how this information will be recorded are given in [section 6.4](#).

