7.2 Specific analysis procedure

The approach is to evaluate the separate platforms (Multiplate/preop; ROTEM; TEG; Multiplate/postop) individually in the first instance, and then evaluate whether the inclusion of additional platforms would improve this. The reason for considering groups of variables by platform (rather than simply choosing the 'best' subset of variables) is because there is no cost of using extra variables from one platform, but an extra cost of doing a second test. The specific steps are as follows:

- Step 1 Review the prediction achieved by patient characteristics. Define an optimal model based only on "baseline" covariates⁶. There will be a separate model for
- **any CCB** (intra-operative or post-operative) and
 - **post-op CCB** only
- Comment: We expect these models to be consistent with one another, not least because the majority of events (post-op CCPB events) will be common to both models.*
- Step 2 Review of each test platform to obtain the best model for each, including the baseline covariates:
- pre-operative Multiplate in relation to **any CCB** (this model is interesting in its own right, but from a slightly different perspective, i.e. it allows the care team to make a plan to mitigate the risk of CCB or to prepare to manage it)
 - pre-operative Multiplate in relation to **post-op CCB**
 - post-operative Multiplate in relation to **post-op CCB**
 - post-operative ROTEM in relation to **post-op CCB**
 - post-operative TEG in relation to **post-op CCB**
- Comment: Each of these models will consider all variables for the test/timepoint, i.e. consider the test/timepoint as a "package." The first model stands alone for **any CCB**. For **post-op CCB**, this step will identify which of the latter four models is the best platform for predicting CCB, i.e. provides the best prediction. We hypothesise that the best platform will be one of the post-op platforms because the information from these is more 'proximal' to the outcome for these models, i.e. **post-op CCB**.*
- For the best test/timepoint** (assuming there is one best test), we will also investigate whether a model using test variables that are available early (for the test identified as best) performs as well as a model using the standard test variables available at "test completion."

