7.4.3 Analysis models

All outcomes listed in the study protocol will be presented as per the template tables [Table T7 to T8](#). General methods of presentation are outlined below.

⁷ i.e. factors associated with the both the laboratory test result(s) (exposure) and the outcome, unbalanced across the groups and not an intermediary step in the causal pathway from the exposure to outcome

The primary outcome (CCB) and secondary outcomes (any RBC transfusions > 4 units RBC transfusion, non-routine pro-haemostatic treatments, death, MI, any stroke, renal failure, AKI and infections during hospital admission) are all binary data.

These binary outcomes will be presented as numbers and percentages of patients. The association between laboratory test results and outcome will be quantified using logistic regression for binary data. Estimates will be presented as unadjusted and adjusted odds ratios (OR) and 95% confidence intervals (95% CI). For these binary outcomes analyses will only be performed if more than ten patients in total experience the outcome.

The sensitivity and specificity of laboratory test results to predict the outcome will be described for different thresholds and laboratory tests will be compared using the area under the receiver operating characteristic (ROC) curve.

The association between time of withdrawal of P2Y₁₂ blocker and laboratory test results will be described using linear regression.

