7.4.8 Missing data

In all tables missing data will be indicated by footnotes. If the amount of missing data differs substantially by outcome, the potential reasons will be explored.

Missing predictors or missing outcomes:

- If the proportion of missing data is less than 5% then complete case analysis will be performed (i.e. excluding cases with missing data).
- If the proportion of missing data is between 5% and 25%, marginal mean imputation will be performed. This involves imputing the most common category in the case of categorical data and the overall median or mean in the case of continuous data.
- If the proportion of missing data is above 25%, multiple imputation methods will be considered. A general imputation model that uses an iterative procedure to generate imputed values will be used to generate multiple complete data sets (e.g. using Stata's `mi impute`). The model of interest will be fitted to each of the complete data sets and effect estimates combined using Rubin's rules.

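### Sections 3.3 and 3.6 can be read as different analysed groups, and no common patient set is fixed for the Step 2 ranking of Models 2B to 2E, so the best-platform choice may be biased or less precise

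*SAP*

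**What the plan says.** Section 3.3 lists groups for judging representativeness. The last is "Consented patients who did provide a post-operative blood sample where at least one laboratory test result was available". The text that follows plans "Formal statistical comparisons of the final analysis group compared to those eligible and not included in the analyses", without defining that final group.

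Section 3.6 begins with a wide rule: "The analysis population will be defined as all eligible, consenting patients who provided a post-operative blood sample". It then narrows it: "The final datasets will be restricted to those with laboratory assay results from the post-operative sample", without saying whether any result or all results are needed. Finally it compares the final population with patients who have outcome data, "a pre-operative sample taken but incomplete laboratory assay results will be compared using standardised mean differences".

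Section 7.2, Step 2, fits pre-operative Multiplate (2B), post-operative Multiplate (2C), ROTEM (2D) and TEG (2E) to post-op CCB and states that "this step will identify which of the latter four models is the best platform for predicting CCB". Section 7.4.3 gives the yardstick: "laboratory tests will be compared using the area under the receiver operating characteristic (ROC) curve".

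Section 7.4.8 handles missing predictors in three bands. In the lowest, "If the proportion of missing data is less than 5% then complete case analysis will be performed". From 5% to 25% the overall mean, median or commonest category is imputed. Above 25%, multiple imputation is to be considered.

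**The concern.** A patient with Multiplate but no TEG result belongs to the last group of 3.3, yet seems to fall outside the final population of 3.6. Section 4.2 (Step 6) foresees such patients, since it plans to review cases with only FBC or Multiplate results.

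The 3.6 comparison is also tied to a pre-operative sample, although the population rests on the post-operative one. Nothing in 3.3 or 3.6 requires a pre-operative Multiplate result, which Model 2B needs.

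This matters because Step 2 picks a winner. The AUC of a baseline score plus tests depends on the case mix in which it is measured and on how absent results are filled in. If either differs between platforms, part of the AUC difference has nothing to do with the tests. Section 7.3 forces the same baseline score into every model so that models can be compared, and an unstated patient set works against that aim.

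**Working it through.** **1. Who is analysed.** Take a patient with a post-operative sample, a Multiplate result and no TEG result.

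| Text | Status |
|---|---|
| 3.3, last group | in |
| 3.6, first sentence | in |
| 3.6, restriction to those with assay results | in if any result suffices, out if all are needed |
| 3.6, comparison with incomplete results | out, by implication |

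On the strict reading, Models 2C, 2D and 2E share their patients, and only 2B can differ. On the loose reading, all four can differ.

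**2. What 7.4.8 does on the loose reading.**

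| Missing on a platform | SAP rule | Effect on the ranking |
|---|---|---|
| below 5% | complete case | patients may differ by platform |
| 5% to 25% | mean, median or mode imputed | same patients, but the imputed value carries no information |
| above 25% | multiple imputation considered | patients differ if it is not used |

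**3. Size.** The SAP gives no missing rate or mechanism, so there is no figure of its own to reproduce. The following is an illustration. Apart from N = 2400 (the study size in 3.1), every input is assumed.

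- Baseline score b and tests A and C are standard normal. A and C share a component with weight 0.6, so their correlation is 0.6² = 0.36.
- Logit of CCB risk = −1.2 + 0.7b + 0.5A + 0.5C, so A and C are equally good.
- Each model's score is 0.7b + 0.68 × test, because 0.5 × (1 + 0.36) = 0.68.
- A is complete. C is missing in 3%, 10% or 20%. There are 600 runs per setting.

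A fair procedure ranks A first in 50% of runs. The Monte Carlo error is √(0.5 × 0.5/600) = 0.020, or about ±4 points at 95%.

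Share of runs with A first, using the rule that 7.4.8 prescribes at each rate:

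| Why C is missing | 3%: complete case | 10%: mean | 20%: mean |
|---|---|---|---|
| at random | 50% | 72% | 90% |
| high baseline risk | 67% | 70% | 90% |
| both extremes of baseline risk | 75% | 64% | 80% |
| abnormal result | 67% | 98% | 100% |

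With random missingness, mean filling gives an AUC gap of 0.006 at 10% and 0.0126 at 20%, roughly in proportion to the share filled in. With SDs of 0.0099 and 0.0103, Φ(0.006/0.0099) = Φ(0.61) ≈ 0.73 and Φ(0.0126/0.0103) = Φ(1.22) ≈ 0.89, which agree with the simulated 72% and 90%. Other assumed inputs gave 59% and 73%, so the direction holds but the size varies.

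In patients with both results, A came first in 47% to 52% of runs when missingness was random or followed baseline risk. When C was missing because it was abnormal, the share was still 60%, 70% and 81% at 3%, 10% and 20% missing.

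**4. Above 25%, without multiple imputation.** A second simulation used 2000 patients, tests correlated 0.6, 5% missing on one platform and 30% on the other. Missing results were 2.5 times as frequent as average in the top 30% of baseline risk. The AUC difference was biased by 0.022 towards the more complete platform, and unbiased in the common set.

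**5. Precision.** In that second setting with random missingness (10% to 30% on the less complete platform), the SD of the AUC difference was 0.006–0.007 in the common set and 0.008–0.010 in separate sets. In the first setting there was almost no loss (0.0105 against 0.0104 at 10%). The loss depends on how strongly the tests are correlated.

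**The case against.** The strongest reply is that the contradiction is inferred. Section 3.3 describes groups for representativeness and does not call the last one the analysis population. Section 3.6 nowhere says that all results are required; that comes from one word in a descriptive comparison. Platform-specific datasets would fit both sections. This stands as far as it goes: the conflict is between readings, not between two stated rules. The text still does not settle which reading applies.

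Second, 7.4.8 keeps patients in at 5% to 25% missing, so differing patient sets do not follow automatically. That also stands, but keeping patients by mean filling does not make the ranking fair.

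Third, section 7.3 compares each model with a baseline-only model. A rerun of the second simulation, with risk-related missingness at 10%, 20% and 30%, gave a raw AUC bias of 0.002, 0.009 and 0.021. For the gain over baseline in the same patients it gave −0.001, −0.002 and −0.007, and the gain showed no loss of precision under random missingness. So the size and even the direction depend on the metric. The SAP does not make the gain its ranking criterion: Step 2 speaks only of best prediction, and 7.4.3 names the AUC.

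Fourth, section 7.4 expects assays on the vast majority of samples, done in a separate laboratory blinded to CCB status. This makes a large effect less likely but gives no figure.

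Finally, the pre-operative SAP, which is not shown, may say more about pre-operative samples. It cannot settle how this document's 3.6 reads.

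**Conclusion.** The point holds as an ambiguity with a consequence. Sections 3.3 and 3.6 admit different analysed groups, the 3.6 comparison names a sample that does not fit its population, and Step 2 has no common patient set. The ranking may therefore be biased or less precise.

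A reader might infer that the best-platform choice is biased. The documents do not support that. On complete cases, bias needs missingness related to risk or result, and random missingness gave 50%. The firmer finding is that the 5% to 25% rule handicaps the less complete platform even under random missingness. That applies only if a platform falls in that band and the loose reading of 3.6 is used.

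A reader might also infer that Steps 2 to 4 are all exposed in the same way. Steps 3 and 4 inherit the Step 2 winner, but they test adding a platform to an existing model, and the likelihood ratio tests preferred in 7.4.4 need the same patients in both models. Mainly the Step 2 ranking is exposed.

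The simulated sizes rest on assumed missing rates, mechanisms and effect strengths. The models were scored with fixed coefficients, without the fractional polynomials and backward elimination of 7.3.

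**What to change.** - State one population rule, in the same words, in 3.3 and 3.6, saying whether any or all post-operative results are required.
- Correct the pre-operative sample in the 3.6 comparison, or justify it.
- For the Step 2 ranking, state that it overrides the marginal mean rule of 7.4.8. Compare Models 2B to 2E by paired AUC differences in patients with results from all four platform/timepoints and a scorable CCB, or in one joint multiple imputation.
- Report n for each model, and show each platform's full-set result as a sensitivity analysis.

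The cost is SAP wording, one population flag and a smaller ranking set. If each of the four were missing independently in 3%, 10% or 20% (assumed), the set would keep 0.97⁴ = 89%, 0.90⁴ = 66% or 0.80⁴ = 41% of patients. It would keep more if results tend to be missing together. If the loss is large, joint multiple imputation is the better option. A common set does not fully remove bias when results are missing because they are abnormal, so the reasons for missing results should be reported by platform.

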4. COPTIC DATA COLLECTION

4.1 Data sources

Information will be collected from the following sources:

Data sources and identification details for linkage

Data type	Brief description	Identification for linkage
CRF Data	Information on time samples were taken, time of CICU admission, blood loss 6 and 12 hours post CICU admission, red blood cells (RBC) and non-RBC transfusions during operation and post-	STUDYID (identifies patient), COPTIC SAMPLEID (identifies sample), operation date, Hospital number/BRI Trust number

STATISTICAL ANALYSIS PLAN

COPTIC: Coagulation and platelet laboratory testing in cardiac surgery
A prognostic study of associations between post-operative test results
and subsequent bleeding

Data type	Brief description	Identification for linkage
	operatively up to CICU admission.	
Clinical data	Data extract from PATS Database including reoperation details (Section 5.1 (iii) and clinical outcomes as detailed in Section 2.5 (c).	Hospital number/BRI Trust number, name, sex, date of birth, operation date
Clinical data	Data extract from INNOVIAN, clinical information system of hourly data for time spent in CICU. These data include red blood cells (RBC) and non-RBC transfusions during CICU admission and clinical outcomes as detailed in Section 2.5 (c).	Hospital number/BRI Trust number, operation date
Clinical data	Creatinine test results for all consenting COPTIC patients, restricted to the closest test prior to the operation (pre-op) and any tests after the operation but within 7 days of the operation date (post-op)	BRI Trust number, date of birth
Laboratory test results	Results from all laboratory tests detailed in Section 2.5.1. These are transferred from the coagulation lab as a single file (FBC) or in the form of many separate files of weekly results (Multiplate, TEG and ROTEM).	All post-operative samples are identified by the COPTIC SAMPLEID (as in CRF data). The date of test will also be used to aid linkage.

4.2 Data linkage

Data from the sources detailed in the above Table will be individually matched in the following order, by the process outlined below:

Step 1 COPTIC CRF data will be linked with the clinical data as stored in PATS. Linkage will be achieved by matching against increasingly liberal matching criteria (i.e. relaxing the criteria required to accept a match), in the following order:

1. Matching on full name, date of birth and hospital number/BRI Trust number
2. Matching on full name and hospital number/BRI Trust number
3. Matching on full name and date of birth
4. Matching on hospital number/BRI Trust number, surname, date of birth (first name probable)
5. Matching on hospital number/BRI Trust number, first name, date of birth (surname probable)
6. Matching on hospital number/BRI Trust number and date of birth

The criteria that are the basis for each match (i.e. 1 to 6 above) will be recorded in the dataset. Records that do not match on operation date will be investigated, and excluded if differences are found to be correct. Instances where no matches can be found within PATS for COPTIC patients will be thoroughly scrutinised.

Step 2 All creatinine test results for tests completed between 27/3/2010 and 31/8/2012 provided by level 8, BRI, will be linked with the PATS and COPTIC file by Trust number and date of birth, and restricted to consenting COPTIC patients. Two separate datasets will be created:

STATISTICAL ANALYSIS PLAN

COPTIC: Coagulation and platelet laboratory testing in cardiac surgery
A prognostic study of associations between post-operative test results
and subsequent bleeding

- The sample relating to the closest time point prior to the operation date and time will be stored and referred to as the baseline creatinine measurement. If this is not available, the pre-operative creatinine value recorded in PATS will be used instead. This dataset will contain the pre-operative (baseline) creatinine measurement.
- The samples taken within 7 days of the operation date will be stored and formatted so these data are suitable for linkage back with the original dataset. This dataset will contain the post-operative creatinine measurements.

Step 3 Linked COPTIC CRF and PATS data will then be linked with the clinical data extracted from INNOVIAN. Linkage will be achieved by matching against increasingly liberal matching criteria (i.e. relaxing the criteria required to accept a match), in the following order:

1. Matching on operation date, hospital number/BRI Trust number
2. Matching on hospital number/BRI Trust number
3. Matching on operation date

The criteria that are the basis for each match (i.e. 1 to 3 above) will be recorded in the dataset. Records that only match on one common factor (2 and 3 above) will be investigated, and excluded if differences are found to be correct. Instances where no matches can be found within INNOVIAN for COPTIC patients will be thoroughly scrutinised.

Step 4 The linked dataset from Step 3 (CRF, PATS and INNOVIAN) will be linked with the creatinine datasets created in step 2.

Step 5 The linked dataset from Step 4 (CRF, PATS, INNOVIAN and creatinine data) will be linked with the FBC laboratory test results dataset, using the SAMPLEID variable. The date of test will be used to verify that the linkage was correctly undertaken. Any discrepancies between dates, or samples without a linked FBC result, or FBC results that do not link to COPTIC samples will be investigated thoroughly. Paper reports will be scrutinised to assist with correct values where duplicate values in the electronic files exist. Results arising from samples which were taken in error will be deleted. Any ambiguities or uncertainties arising during linking data through this step will consider findings and inconsistencies recorded in the Lab Deviation files.

Step 6 The linked dataset from Step 5 (CRF, PATS, INNOVIAN, creatinine and FBC results) will be linked with the Multiplate laboratory test results dataset, using the SAMPLEID variable. The date of test will be used to verify that the linkage was correctly undertaken. Any discrepancies between dates, or samples without a linked Multiplate result, or Multiplate results that do not link to COPTIC samples will be investigated thoroughly. Instances where only FBC or Multiplate results are available will also be reviewed. Paper reports will be scrutinised to assist with correct values where duplicate values in the electronic files exist. Results arising from samples which were taken in error will be deleted. Any ambiguities or uncertainties arising during linking data through this step will consider findings and inconsistencies recorded in the Lab Deviation files.

Step 7 The linked dataset from Step 6 (CRF, PATS, INNOVIAN, FBC and Multiplate results) will be linked with the ROTEM laboratory test results dataset, using the SAMPLEID variable. The date of test will be used to verify that the linkage was correctly undertaken. Any discrepancies between dates, or samples without a linked ROTEM result, or ROTEM results that do not link to COPTIC samples will be investigated thoroughly. Paper reports will be scrutinised to assist with correct values where duplicate values in the electronic files exist. Results arising from samples which were taken in error will be deleted. Any ambiguities or uncertainties arising during linking data through this step will consider findings and inconsistencies recorded in the Lab

Deviation files.

- Step 8** The linked dataset from Step 7 (CRF, PATS, INNOVIAN, FBC, Multiplate and ROTEM results) will be linked with the TEG laboratory test results dataset, using the SAMPLEID variable. The date of test will be used to verify that the linkage was correctly undertaken. Any discrepancies between dates, or samples without a linked TEG result, or TEG results that do not link to COPTIC samples will be investigated thoroughly. Paper reports will be scrutinised to assist with correct values where duplicate values in the electronic files exist. Results arising from samples which were taken in error will be deleted. Any ambiguities or uncertainties arising during linking data through this step will consider findings and inconsistencies recorded in the Lab Deviation files.

In addition, data regarding the administration of anti-fibrinolytic drugs, recombinant human coagulation factors VII (rFVII) or fibrinogen concentrate will be provided by the Haematology department and checked against the data recorded in PATS. If there are any discrepancies, the data provided by the Haematology department will be used.

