6.2 Secondary endpoints

New variable	Rules	Data sources
RBC transfusion	Any RBC transfusion during interval 2	INNOVIAN clinical information

⁵ Diagnosis, evaluation, and management of acute kidney injury: a KDIGO summary (Part 1). Kellum *et al.* Critical Care 2013, 17:204

STATISTICAL ANALYSIS PLAN

COPTIC: Coagulation and platelet laboratory testing in cardiac surgery
A prognostic study of associations between post-operative test results and subsequent bleeding

New variable	Rules	Data sources
(binary)	(the time between post-operative samples are taken and discharge from CICU).	system
RBC >4 units (binary)	Any RBC transfusion >4 units during interval 2 (the time between post-operative samples are taken and discharge from CICU).	INNOVIAN clinical information system
Non-routine pro-haemostatic treatments (binary)	Any platelet, FFP, cryoprecipitate or rFVII transfusion during intervals 1 and 2 (the time between post-operative samples are taken and discharge from CICU), or therapeutic protamine during interval 2b (the time between post-operative samples are taken and 12 hours post CICU-admission).	INNOVIAN clinical information system and CRFs
Serious post-operative complications:		
Death (binary)	Vital status (alive vs. died in theatre OR died in hospital).	PATS Database (updated with NSTS data)
MI (binary)	Any MI occurring before discharge OR death from MI in hospital.	PATS Database, INNOVIAN clinical information system and death certificate data
Stroke (binary)	Any peri- OR post-operative neurological complication (stroke; transient ischaemic attack; hemiplegia; paralysis; paraplegia; dysphasia; cerebral/CNS infarct/embolus).	PATS Database, INNOVIAN clinical information system
AKI (binary)	Serum creatinine increased by ≥ 26.5 $\mu\text{mol/l}$ from the pre-operative value within 48 hours of surgery OR serum creatinine increased ≥ 1.5 times the pre-operative value within 7 days of surgery.	Creatinine data
Infection during hospital admission (binary)	Any infective complication (chest infection; wound infection; mediastinitis; graft site infection; sternal wound infection; urinary tract infection; septic; sepsis; blood borne infection).	PATS Database and INNOVIAN clinical information system

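### The creatinine extract ends on the last day of the surgery period, so the AKI window is incomplete for operations on 25–31 August 2012 and some AKI may be scored as absent

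*SAP*

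**What the plan says.** Section 3 defines the population as adults "attending Bristol Heart Institute for cardiac surgery between 30 March 2010 and 31 August 2012".

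Section 4.2, Step 2, takes "All creatinine test results for tests completed between 27/3/2010 and 31/8/2012" and splits them into a baseline set and a post-operative set. For the latter, "The samples taken within 7 days of the operation date will be stored". A missing baseline value falls back on the creatinine recorded in PATS. No fallback is given for post-operative values.

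Section 6.2 makes AKI a binary variable with two limbs. One is an absolute rise "from the pre-operative value within 48 hours of surgery OR serum creatinine"; the other is a rise to at least 1.5 "times the pre-operative value within 7 days of surgery". The only source listed there is the creatinine data. Section 5.3 repeats the definition and explains that creatinine-based AKI replaced new dialysis because PATS was too incomplete.

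Section 5.2, by contrast, says that the secondary outcomes count as having occurred on positive evidence in PATS or INNOVIAN, free text included, and it lists renal search terms.

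**The concern.** Three statements cannot all hold: surgery up to 31 August 2012, an outcome that needs creatinine for 7 days after surgery, and an extract that stops on 31 August 2012. The extract starts three days before the surgery period but has no margin at its end.

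The resulting loss runs in one direction. A cut window can hide a qualifying rise, but it cannot create one. A patient operated on 29 August with an unremarkable value on 30 August has post-operative data and no recorded rise. Section 6.2 gives only the positive criterion and says nothing about incomplete observation, so such a patient could well be coded as having no AKI. The missing-data rules in section 7.4.8 would not act if nothing is flagged as missing. At stake is the AKI count, and the logistic regression of AKI on the laboratory results (section 7.4.3), for a small and identifiable group.

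**Working it through.** The SAP gives no figure on this point, so there is nothing to reproduce. The check is date arithmetic followed by a sizing.

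**Inputs from the SAP**
- Surgery period: 30 March 2010 to 31 August 2012 (section 3)
- Last date in the creatinine extract: 31 August 2012 (section 4.2)
- AKI windows: 48 hours and 7 days (section 6.2)
- Planned sample: 2400 over a planned 2-year period (section 3.1)

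**Assumed, not in the SAP**
- AKI risk *p*: 10–30%
- Share *f* of AKI in the affected group first evident after the cut-off: 10–50%
- Even recruitment over time

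**Step 1: which operations are cut.** A full window needs operation date + 7 days ≤ 31 August 2012, so the last date with a full 7-day window is 24 August. In the same way, the last date with a full 48-hour window is 29 August.

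| Operation date (August 2012) | Days of extract after it | 7-day window | 48-hour window |
|---|---|---|---|
| 25 | 6 | cut | complete |
| 26 | 5 | cut | complete |
| 27 | 4 | cut | complete |
| 28 | 3 | cut | complete |
| 29 | 2 | cut | complete |
| 30 | 1 | cut | cut |
| 31 | 0 | cut | cut |

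**Step 2: how many patients.** The surgery period has 886 days inclusive. The planned 2 years have 730.
- 7 / 886 = 0.79%; 2400 × 7 / 886 = 19.0 patients
- 7 / 730 = 0.96%; 2400 × 7 / 730 = 23.0 patients

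The analysis set under section 3.6 is a subset of recruited patients. With even recruitment, the count falls in proportion and the percentage stays the same.

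**Step 3: how many AKI cases might be missed.** Expected number = affected patients × *p* × *f*.
- Lowest: 19.0 × 0.10 × 0.10 = 0.19
- Highest: 23.0 × 0.30 × 0.50 = 3.45

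The chance of missing at least one case is 1 − (1 − *pf*)^n.
- Lowest: 1 − 0.99^19 = 0.17
- Highest: 1 − 0.85^23 = 0.98

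So at least one missed case is plausible but not certain.

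**Step 4: end date that removes the problem.** 31 August 2012 + 7 days = 7 September 2012.

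**The case against.** The date conflict itself is hard to dispute. The case on the other side concerns its consequence.

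- **No stated scoring rule.** A reader might infer that AKI will be recorded as absent whenever later creatinine is lacking. The SAP does not say so. A patient with no post-operative value at all could be treated as having a missing outcome and dropped under the complete-case rule in section 7.4.8. For a partly observed window the SAP is silent, and scoring as absent is only the likely default. This objection stands, and it is why the point says *may*.
- **Another route to AKI.** Section 5.2 would let PATS or INNOVIAN evidence count, which might recover some cases. The route is uncertain: section 6.2 names creatinine data alone, section 5.3 calls PATS incomplete, and section 4.1 describes INNOVIAN as covering time in CICU, so a later rise on the ward could escape it. The objection stands in part, and it exposes a second inconsistency.
- **Size.** A reader might take all AKI expected in the final week as lost, that is 19.0 × 0.10 = 1.9 to 19.0 × 0.30 = 5.7 cases. That would require none of it to show by 31 August. Yet operations on 25–29 August keep the whole 48-hour window, and an operation on 25 August keeps 6 of its 7 days.
- **Intent.** Section 4.1 describes post-operative creatinine as any test in the 7 days, with no calendar limit. The intention is clear, but Step 2 as written does not deliver it.

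**Conclusion.** The dates in sections 3, 4.2 and 6.2 contradict each other. That much is certain and rests on no assumption. Seven operation dates have an incomplete 7-day window, and two of them also have an incomplete 48-hour window.

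The effect is small: 0.8 to 1.0% of patients on one secondary outcome. The 0.2 to 3.5 missed cases depend on the assumed AKI risk and timing and on even recruitment; they also take an unseen rise to be coded as no AKI, with none recovered from PATS or INNOVIAN. The true number could be zero. The definition of clinical concern about bleeding does not use creatinine after surgery, so neither the primary outcome nor the platform comparison in section 7.2 is touched. This is a minor correction, worth making because the error is specific and can only lose events.

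**What to change.** 1. In section 4.2, Step 2, change the end of the creatinine extract to at least 7 September 2012. No operation in the surgery period then has a cut window. The cost is one repeat of the extract and its linkage, if the data can still be drawn. The SAP does not show whether they can, and its amendments are dated 2013 to 2015. If the extract actually ran later than stated, correcting the date is enough.
2. In the same edit, make sections 5.2 and 6.2 agree on whether PATS and INNOVIAN evidence counts towards AKI or creatinine alone defines it. This costs one sentence.
3. If the data cannot be re-drawn, exclude all patients operated on 25–31 August 2012 from the AKI analysis, whatever their observed result. This costs about 1% of patients for this outcome only.

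Do not set only the AKI-negative patients in that week to missing. Under complete-case analysis the week would then contribute AKI-positive patients alone, so missingness would depend on the outcome. If missing AKI overall reached 5–25%, section 7.4.8 would impute the most common category, probably no AKI, and undo the correction.
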